2.0 Background/Scientific Rationale

Residual limb hip muscle weakness is a pronounced, consequential, and modifiable deficit among prosthesis users that is not adequately understood. After amputation residual limb hip muscles undergo structural changes, such as atrophy^{1,2,3} and fatty infiltration^{4,3}, causing pronounced muscle weakness^{2,5-7}. These changes are not observed with the same frequency or magnitude in the intact leg⁵, suggesting they are due to amputation¹³ and/or socket design⁹ rather than general deconditioning⁵. Assessments of residual limb strength have, to date, however been limited to non-fatiguing conditions, and measures of maximum voluntary strength^{2,5,6}. Important functional aspects of strength including the rate of force development, which is essential to balance¹⁰⁻¹¹, and muscular endurance, which is crucial to mobility^{12,31} and strenuous tasks like load carriage¹², have been overlooked. Additionally, a number of major residual limb hip muscles and relevant covariates (e.g., etiology) remain untested. As a result, we do not have a full understanding of the force generating capacity of residual limb hip muscles in transfemoral prosthesis users that is required to assess the effect of socket design on residual limb hip muscle function. To address this gap a comprehensive evaluation of residual limb hip muscle strength and endurance is needed.

Preliminary evidence suggests residual limb hip muscle weakness is a consequential deficit among transfemoral prosthesis users. Muscle weakness has been associated with gait abnormalities^{1,13}, secondary degenerative disorders (e.g., joint degeneration)¹⁴, increased metabolic cost of gait^{15,16}, as well as reduced mobility^{17,18} and balance confidence¹⁹. Causal links however between residual limb hip muscle function and balance or mobility remain poorly understood among transfemoral prosthesis users²¹. Preliminary statistical modeling of causal relationships between residual limb hip muscle function and walking and balance performance is needed to address this gap.

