3.0 Objectives/Aims

The objective of this study is to assess residual limb hip muscle function in lower limb prosthesis users, understand its role in balance and mobility, and the effect of socket design on residual limb hip muscle function. Our central hypothesis is that the residual limb is weaker than the intact limb as well as controls, and that socket design alters hip muscle function. To address this objective and central hypothesis, we will assess the following specific aims:

Aim 1: Evaluate hip muscle function and its contribution to balance and mobility among unilateral lower limb prosthesis users. We hypothesize that: i) the strength and endurance of hip muscles on the residual limb will be lower than on the intact limb, and of age- and sex-matched able-bodied persons, and ii) muscular strength and endurance will not differ between the intact limb and age- and sex-matched able-bodied persons. To test these hypotheses hip muscle strength and endurance will be measured using a motor-driven dynamometer. Lower peak torque and rates of torque development will be taken as evidence of reduced strength, while a larger decrease in average work at the end of an isokinetic fatigue protocol will be taken as evidence of reduced endurance. Secondarily, we will also collect balance and mobility outcomes data (e.g., Four Square Step Test, PLUS-M, step counts, and fall history), and use regression methods to explore the contributions of hip muscle strength and endurance to balance and mobility in lower limb prosthesis users.

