4.3 Excluded or Vulnerable Populations

Subjects younger than 18 and older than 85 years of age will be excluded, as their inclusion would introduce confounding factors of sensorimotor changes due to motor development and aging.

Subjects for whom English is a second language will also be excluded because there are extensive verbal instructions that must be provided to the participants. Translation services are not readily available to assist laboratory personnel. Participants will also be expected to provide information via self-report survey instruments that have not been translated and/or validated in other languages.

Individuals with bilateral lower limb loss and any upper extremity limb loss will be excluded, as their biomechanics are not comparable to individuals with unilateral lower limb loss.

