12.0 Statistical Considerations

Descriptive statistics: Measures of central tendency and variation will be used to describe participant characteristics, and all study variables (e.g., balance and mobility tests, muscle strength). Normality, homogeneity of variance, and multicollinearity will be evaluated using the Shapiro-Wilk test, Levene's test, and, Pearson's r (r<.90) respectively. If assumptions are met data will be analyzed with parametric tests, otherwise non-parametric tests will be used. Statistical analyses will be performed using SPSS 25 (Chicago, IL).

Aim 1: A 2-way mixed-MANCOVA (multiple analysis of covariance), or non-parametric equivalent, will be used to test for statistically significant differences in strength and endurance between legs (prosthetic, intact, and control) as well as across muscle groups while controlling for potential covariates (e.g., residual limb length, etiology). Multiple linear regression will be used to determine how much variation (i.e., difference) in balance and mobility outcomes (e.g., Four Square Step Test; physical activity) among transfemoral prosthesis users can be explained by differences in hip muscle strength and endurance.

Aim 2: As a pilot study, descriptive analyses including measures of central tendency (mean) and dispersion (95% confidence intervals), along with effect sizes (e.g., Cohen's d, common

language effect size), will be used to evaluate changes in residual limb hip muscle activity, strength, between test sessions while controlling for covariates. Correlation analyses will be used to determine if any observed changes in hip muscle strength can be attributed to changes in hip muscle activity (i.e., EMG) or physical activity (i.e., step count).

Power Analysis: Choosing a power of 0.80 and a type I error rate (α) of 0.05, pilot data from lower prosthesis users (n=2) and able-bodied persons (n=2) estimate that a sample of 20 people per group will be sufficient to identify differences (p<0.05) in hip muscle strength and endurance between the residual limb, intact limb, and able-bodied persons using a mixed analysis of variance (ANOVA) (Aim 1). As a pilot study, enrollment in Aim 2 will be limited to 10 unilateral lower limb prosthesis users.

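### The Aim 1 regression of balance and mobility on hip strength names no adjustment for age across 18 to 85 years, and no suitable model is named for yes/no fall history

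*Combined protocol and SAP*

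**What the plan says.** Section 12.0 gives Aim 1 two analyses. The first, a mixed MANCOVA comparing legs and muscle groups, is to be done "while controlling for potential covariates (e.g., residual limb length, etiology"; age is not among those examples. The second is the regression: "Multiple linear regression will be used to determine how much variation (i.e., difference) in balance and mobility outcomes" "among transfemoral prosthesis users can be explained by differences in hip muscle strength and endurance", with the Four Square Step Test and physical activity as example outcomes. No covariate is attached to it.

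Other sections bear on it:

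- Section 4.3 sets the age limits ("Subjects younger than 18 and older than 85 years of age will be excluded") on the ground that including people outside them "would introduce confounding factors of sensorimotor changes due to motor development and aging".
- Section 2.0 gives the purpose: "Preliminary statistical modeling of causal relationships between residual limb hip muscle function and walking and balance performance is needed". Section 3.0 describes the work as secondary and as exploring what hip strength and endurance contribute.
- Section 3.0 lists the balance and mobility outcomes as "e.g., Four Square Step Test, PLUS-M, step counts, and fall history", to be studied by regression methods of no stated type.
- Section 6.0 (Characterization Measures) records age. It obtains falls history by asking whether the participant fell in the past year, which invites a yes or no and requests no count.

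**The concern.** Age is a plausible common cause of weak hips and poor balance. The age limits leave nearly the whole of adult ageing in the sample. Two features of the design might seem to deal with this but do not. Age- and sex-matching concerns the able-bodied controls and does nothing within a regression confined to prosthesis users. Strength values are normalized to body weight, not to age.

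If age is left out, an R-squared for strength mixes what strength adds with what strength merely shares with age. A larger sample would not remove this, so it is a different problem from overfitting. At stake is the answer to the secondary Aim 1 question, and any later argument that strengthening the hip would improve balance.

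Fall history raises a question of model form: a yes/no outcome has no suitable model in the statistical section.

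**Working it through.** **The plan's own figure.** The only sample size is 20 per group (power 0.80, alpha 0.05) for a mixed ANOVA, from pilot data with n=2 per group. No effect size or SD is given, so it cannot be reproduced. Solved backwards for two means with a two-sided normal approximation, it implies d = (1.960 + 0.842) × √(2/20) = 0.886. Nothing is stated for the regression, which would have about 20 prosthesis users.

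**Inputs.** From the documents: ages 18 to 85, about n=20, strength and endurance as the predictors named, no covariate named. Assumed, because the documents do not give them: all correlations, path coefficients, odds ratios and fall proportions below.

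**1. No direct strength effect.** On standardized variables, the R-squared credited to strength when age is omitted is (r age-strength × r age-outcome)². With age in the model, strength's unique share is 0. The last two columns give the simulated rejection rate for strength at nominal 5%, n=20 (20,000 runs).

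| Size of both age correlations | Spurious R-squared | Rejection, age omitted | Rejection, age included |
|---|---|---|---|
| 0.3 | (0.09)² = 0.008 | 6.6% | 4.7% |
| 0.5 | (0.25)² = 0.062 | 18.7% | 4.9% |
| 0.7 | (0.49)² = 0.240 | 61.8% | 5.0% |

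If age and strength are uncorrelated, the spurious R-squared is 0 and the rejection rate is 4.9% (with an age-outcome correlation of 0.5).

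**2. A real strength effect.** Take a standardized strength coefficient of 0.3, an age coefficient of -0.5 and an age-strength correlation of -0.5.

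- Strength alone: r = 0.3 + (-0.5)(-0.5) = 0.55, R-squared 0.3025.
- Age alone: r = -0.5 + 0.3(-0.5) = -0.65, R-squared 0.4225.
- Both: 0.25 + 0.09 + 2(0.3)(-0.5)(-0.5) = 0.49.
- Increment for strength after age: 0.49 - 0.4225 = 0.0675.

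Strength is credited with 30% alone and 6.8% beyond age. With the age coefficient and age-strength correlation both at -0.3, the pair is 15.2% and 8.2%. With the correlation at -0.7 and the age coefficient at -0.5, it is 42% and 4.6%.

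**3. Precision of the increment.** In the scenario of step 2 at n=20, with sex also entered as an unrelated covariate, the increase in adjusted R-squared had a 95% sampling range of -0.04 to 0.32 and was negative in 31% of samples.

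**4. A straight line for a yes/no outcome.** At n=20 with one predictor and fall proportions of 0.5 and 0.3, at least one fitted value fell outside 0 to 1 in 32% and 41% of runs at an odds ratio of 0.5 per SD, and in 72% and 76% at 0.25 (5,000 runs each).

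**The case against.** The strongest reply is that the plan asks how much variation strength can explain. Read descriptively, the unadjusted R-squared answers that. The analysis is secondary, exploratory and called preliminary, and if ageing harms balance partly through loss of hip strength, the shared variation is a pathway, not an error. This stands in part: it is a reason to report results both with and without age. It does not justify reporting only the unadjusted figure, given the causal purpose in section 2.0.

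The plan's silence is also not an exclusion. Section 12.0 states a question and does not close the list of predictors. But the covariate clause belongs to the MANCOVA, and an analyst following the text would have no instruction to add age.

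Four stronger readings are tempting, and the documents do not support them:

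- *That the reported contribution is certain to be inflated.* This depends on correlations not given; at 0.3 the effect is trivial, and it can be nil.
- *That all age-related variation goes to strength.* Only the part shared with strength does.
- *That section 4.3 declares age a confounder within 18 to 85.* It refers to "confounding factors of sensorimotor changes due to motor development and aging" to justify the limits. It shows that the authors take ageing seriously, no more.
- *That fall history will be fitted by linear regression.* No sentence says so: section 3.0 leaves the regression type open, and the examples in section 12.0 are not binary.

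Finally, the R-squared increment after age is not the true contribution either. It gives all shared variation to age, and step 3 shows how imprecise it is.

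**Conclusion.** The concern holds as a conditional one. The regression names no age adjustment although its purpose calls for one. If ageing lowers both strength and balance, strength will be credited with variation that it only shares with age. With no direct strength effect, the assumed range of spurious R-squared is about 0.01 to 0.24 for age correlations of 0.3 to 0.7, and zero if age and strength are uncorrelated. The contrast of 30% with 6.8% is one assumed scenario and not an estimate for this study.

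For fall history, the supportable statement is that no suitable model is named. A reader might infer a linear fit because linear regression is the only type specified and the generic fallback to non-parametric tests names no binary model, but that remains an inference.

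Both points concern a secondary analysis and leave the main limb comparisons untouched. They should be settled before the regression is run.

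**What to change.** Add a few sentences to section 12.0:

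- Name in advance one or two strength or endurance predictors. Four muscle groups by three measures gives up to 12 on one limb, and with n=20 the expected R-squared under no association is then already 12/19 = 0.63.
- Include age in the model. Report the age-adjusted strength coefficient and the R-squared increment, each with a confidence interval, beside the unadjusted result. State that the increment is a conservative measure, since shared variation goes to age.
- State that fall history will be analysed by penalized (Firth) logistic regression with one strength predictor, or by comparing strength between fallers and non-fallers with a confidence interval.

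No new data are needed, because age is already collected. The cost is one degree of freedom at about n=20, wide intervals that the report should acknowledge, and probably a smaller reported contribution of hip strength.

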Aim 2: Test whether socket design alters hip muscle function among lower limb prosthesis users. We hypothesize that walking with different socket designs will: i) require different residual limb hip muscle activity, as evidenced by greater peak muscle activity, as well as altered onset and offset times, and ii) result in short- and long-term gains in residual limb hip muscle strength and endurance, as evidenced by an increase in average peak torque, rate of torque development, and resistance to fatigue. To test these hypotheses electromyographic signals will be recorded from hip muscles on the residual limb of unilateral lower limb prosthesis users walking at a range of speeds. Hip muscle strength and endurance will be measured using a motor-driven dynamometer. Assessments will be made at baseline in established wearers of an ischial containment socket, and then again at eight and 42-weeks after being fit with a sub-ischial socket. Step count activity data will be collected to determine the extent to which gains in residual limb hip muscle strength and endurance are due to changes in hip muscle activation versus an increase in physical activity.

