6.0 Study Design and Procedures

Consented individuals will participate in 1 or 3 test sessions. Each session will require approximately 3 hour. For Aim 1, we will conduct a cross-sectional study to evaluate residual and intact limb hip muscle function in lower limb prosthesis users compared to able-bodied persons. All participants will be administered characterization measures, balance and mobility tests, as well as a series of procedures to evaluate hip muscle strength, endurance, and coordination. This will require a single 3-hour test session. Able-bodied controls and lower limb prosthesis users will perform the same activities in Aim 1.

For Aim 2, we will conduct a pilot within-subjects study to assess if walking with a different socket alters residual limb hip muscle function. In Aim 2, a sub-set of lower limb prosthesis users from Aim 1 will walk with a different socket. These participants will be selected on the basis of meeting the inclusion and exclusion criteria specified above for Aim 2. The same measures, tests, and procedures from Aim 1 will be administered in Aim 2 at two time points, eight and 42-weeks after baseline testing. Outcomes at these two time points will be compared to baseline (Aim 1) to evaluate differences in hip muscle function associated with walking in a different socket. Three total test visits will be required of participants in Aim 2.

The tasks listed below will be performed at each visit.

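### Aim 2's change analysis should rest on the unadjusted paired change with its SD, use a small-sample-corrected effect size with a stated denominator, and include endurance (minor).

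*Combined protocol and SAP*

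**What the plan says.** Section 6.0 states that for Aim 2 "we will conduct a pilot within-subjects study to assess if walking with a different socket alters residual limb hip muscle function", and that "Outcomes at these two time points will be compared to baseline (Aim 1) to evaluate differences in hip muscle function", the two time points being weeks 8 and 42. Section 12.0 fixes the size: "enrollment in Aim 2 will be limited to 10 unilateral lower limb prosthesis users".

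The Aim 2 analysis in Section 12.0 is descriptive. It plans "measures of central tendency (mean) and dispersion (95% confidence intervals), along with effect sizes (e.g., Cohen's d, common" language effect size being the second example. These "will be used to evaluate changes in residual limb hip muscle activity, strength, between test sessions while controlling for covariates". The section does not name the Aim 2 covariates, their number, the adjustment model, or the denominator of d. Residual limb length and etiology appear as covariate examples, but only for Aim 1.

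Hypothesis (ii) of Aim 2 in Section 3.0 is that a different socket will "result in short- and long-term gains in residual limb hip muscle strength and endurance". Section 6.0 defines a fatigue index as the endurance measure.

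**The concern.** A 10-person pilot is useful mainly for the size and spread of change that it hands to a later trial. Four features of the Aim 2 sentence weaken that output.

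- Covariate control is carried into a paired comparison where stable personal characteristics already cancel.
- Cohen's d is proposed without a small-sample correction or a stated denominator.
- The confidence interval is described as the measure of dispersion, and the SD of change is not mentioned.
- Endurance, one of the two outcomes in hypothesis (ii), is not listed.

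At stake are a modest loss of precision, a modestly optimistic effect size, and a hypothesised outcome with no stated analysis.

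**Working it through.** **Inputs from the documents.** n = 10 (Section 12.0); each follow-up is compared with baseline in a within-subjects design (Section 6.0); 95% CIs (Section 12.0). The 10 is a pilot cap with no calculation behind it, so there is no planned figure to reproduce.

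**Assumptions, not in the documents.** Normal data, no dropout, equal SDs across sessions, one to three covariate degrees of freedom, within-person correlation r up to 0.9, and d = 0.5 for illustration.

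**1. Covariates fixed within a person.** The change is follow-up minus baseline for the same person, so any constant contribution of limb length or etiology to that person's level subtracts out. Such covariates may predict who changes more, but they cannot confound the mean change. With k mean-centred covariate terms, the 95% CI half-width, taking the residual SD as unchanged, is t(0.975, 9 − k) × SD of change / √10. Adjustment breaks even when the covariates explain a share 1 − [t(9) / t(9 − k)]² of the variance of change.

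| k | t | Half-width (SD of change) | Widening | Break-even share |
|---|---|---|---|---|
| 0 | 2.262 | 0.715 | – | – |
| 1 | 2.306 | 0.729 | 2% | 3.8% |
| 2 | 2.365 | 0.748 | 5% | 8.5% |
| 3 | 2.447 | 0.774 | 8% | 14.5% |

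Limb length plus etiology in the three categories of Section 4.0 would use k = 3. In 20,000 simulations per k (true change 0.50 SD), the estimate stayed unbiased. Average half-widths were 0.695, 0.705, 0.719 and 0.741, a widening of 1%, 3% and 7%. This is slightly below the table because the estimated residual SD is itself a little low at few degrees of freedom.

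**2. Small-sample bias of d.** The Hedges factor is J(m) = Γ(m/2) / [√(m/2) Γ((m − 1)/2)], and uncorrected d is inflated on average by 1/J. Sample size varies as 1/d², so sizing from the inflated value gives J² of the number needed.

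- Paired d (SD of change, 9 df): J = 0.914, 1/J = 1.094, J² = 0.835. Inflation 9.4%, sample size about 16% too small.
- Raw-SD d with r = 0 (18 df): J = 0.958, 1/J = 1.044, J² = 0.917. Inflation 4.4%, sample size about 8% too small.
- Raw-SD d with r = 0.8: simulated inflation about 7%; 1/1.07² = 0.873, so about 13% too small.

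**3. Why the denominator must be stated.** With equal SDs, paired d = raw-SD d / √[2(1 − r)]. The ratio is 1.00 at r = 0.5, 1.29 at 0.7, 1.58 at 0.8 and 2.24 at 0.9. For a raw-SD d of 0.5, the independent-samples common language effect size is Φ(0.5/√2) = 64%. The paired form, Φ(paired d), is 69%, 74%, 79% and 87% at the same correlations.

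**4. Endurance and SD, by comparison of sections.** Section 3.0 hypothesises gains in strength and endurance; Section 6.0 defines the fatigue index and repeats all measures at both follow-ups; the Aim 2 change sentence in Section 12.0 lists muscle activity and strength only. The correlation sentence after it also mentions only strength, whereas Section 3.0 applies the step-count question to both. As to spread, an unadjusted paired CI at n = 10 gives SD = half-width × √10 / 2.262 = half-width × 1.398. An adjusted CI from an unstated model does not allow this.

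**The case against.** The strongest reply is that the plan leaves choices open but does not make wrong ones. Much of that stands, and it rules out three stronger readings.

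- A reader might infer that the plan uses two-sample tools on paired data. Section 6.0 calls the study within-subjects, Section 12.0 analyses changes, and both effect sizes are only examples and have paired forms.
- A reader might infer that the effect sizes are therefore mis-scaled. They are undefined, which is different; a raw-SD d is a legitimate standardisation if labelled as such.
- A reader might infer a collapse of power, from 0.80 to about 0.10, if limb length enters an SPSS repeated-measures model uncentred and the session effect is read at length zero. That needs an assumed model, an assumed covariate mean and SD (10 and 2.5 inches) and a significance test. Aim 2 plans none of these, and a mean change evaluated at the covariate mean is the same whether or not the covariate is centred.

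Further points also have force. Covariates that predict change improve precision. Step count, which Section 3.0 brings into Aim 2, varies over time, so the cancellation argument does not cover it. Section 12.0 promises measures of variation for all study variables, though it does not mention the change scores. The missing endurance term may be a drafting slip, since the list ends on a stray comma. Finally, at n = 10 the CI half-width is about 0.7 SD of change, so sampling error in d far exceeds a 4% to 9% bias.

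The bias remains in every form of d and is easily removed. The text on endurance and on the SD of change still needs correcting.

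**Conclusion.** The point holds as a minor one. Uncorrected d at n = 10 is inflated by about 4% to 9%, which would make a later sample size based on it about 8% to 16% too small. Adjusting for one to three covariate terms fixed within a person removes no confounding of mean change; it costs 2% to 8% of CI width if they explain nothing and pays only above the break-even shares shown. Endurance is absent from the Aim 2 change analysis, and the SD of change is not planned; neither finding depends on any assumption. The numerical results assume normal data, equal session SDs and all 10 participants completing. The covariate result applies to Aim 2 only if its unnamed covariates resemble the Aim 1 examples.

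**What to change.** Reword the Aim 2 paragraph of Section 12.0:

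1. Main estimate: unadjusted mean paired change from baseline at weeks 8 and 42, with the number analysed, the SD of change and a t-based 95% CI.
2. Adjustment: a sensitivity analysis only, with covariates named in advance and centred at their mean.
3. Effect sizes: d with its denominator stated, the Hedges correction and a CI, plus the paired common language effect size. Reporting the within-person correlation lets readers convert between forms of d.
4. Outcomes: add the fatigue index to the change analysis, and to the correlation analysis so that it matches Section 3.0.

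This needs wording changes only, with no new data or visits. The correction makes any given d slightly smaller, and a precision gain from a covariate that does predict change would appear only in the sensitivity analysis.
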